## 6.3.10 Change from Baseline in ASEX Total Score

The ASEX questionnaire measures sexual experience, with categories of sex drive, arousal, vaginal lubrication/penile erection, ability to reach orgasm, and satisfaction from orgasm. Each of the 5 items will be scored from 1-6 and the Total Score will be calculated by summing each component. The total score will range from 5 to 30. Higher scores indicate the presence of sexual dysfunction. Sexual dysfunction is defined as having a total score  $\geq$  19, or a score of  $\geq$  5 on any item, or a score of  $\geq$  4 on three items.

The number and proportion of subjects with sexual dysfunction will be presented by sex at birth and treatment group for each visit. The observed difference in the rates of sexual dysfunction between each dose of MM-120 and placebo, along with the 95% CI for the difference, will be presented by sex at birth for Week 1, Week 2, Week 4, Week 8 and the End of Study visit.

Descriptive statistics, including 95% CIs for the mean, for the ASEX Total Score will be presented for actual values and change from Baseline for scheduled visits by sex at birth. The change from Baseline difference in means between each dose of MM-120 and placebo and 95% CI for the difference will be presented for Week 1, Week 2, Week 4, Week 8 and the End of Study visit. A by-subject listing of results by visit, including sex at birth, will be provided for all ASEX responses and the Total Score.

## 6.4 Exploratory Endpoints and Analyses

The endpoints of Drug Effect VAS, MEQ30 and 5D-ASC will be measured to explore the dose response on drug effects, altered perception and mystical experience. To assess the blind integrity and to examine whether guess rates are associated with outcomes such as AEs or mood/anxiety, a treatment assignment question will be administered.

## 6.4.1 HAM-A Response and Remission

HAM-A response is defined as a decrease from Baseline by  $\geq 50\%$  in HAM-A Total Score in response to treatment, and a Total Score of  $\leq 7$  indicates a remission of symptoms. The number and proportion of subjects with response and with remission will be presented by treatment group for Week 1, Week 2, Week 4, Week 8 and the End of Study visit. The observed difference in the rates of response and remission between each dose of MM-120 and placebo, along with the 95% CI for the difference, will be presented for each visit.

## 6.4.2 Drug Effect VAS

The Drug Effect VAS will be administered on Day 2 to retrospectively assess the subject's perception of drug effects experienced during the dosing session. A series of single-item 100 mm VAS questions will be used to measure the extent to which the subject experienced each of the following:

- 'any drug effect'
- 'good drug effect'
- 'bad drug effect'
- 'drug liking'

- 'nausea'
- 'alteration of vision'
- 'alteration of sense of time'
- 'the boundaries between myself and my surroundings seem to blur'

• 'fear'

Descriptive statistics for each VAS score will be presented for actual values at Day 2. A by-subject listing of results be provided.

## 6.4.3 MEQ30

The MEQ30 will be administered on Day 2 to retrospectively assess the subject's mystical experience during the dosing session. The MEQ30 includes 30 self-rated questions with 4 subscales: mystical, positively mood, transcendence of time and space, and ineffability. Each of the 30 questions will be scored from 0 to 5 as:

- 0 =none; not at all
- 1 =so slight cannot decide
- 2 = slight
- 3 = moderate
- 4 = strong (equivalent in degree to any other strong experience)
- $5 = \text{extreme} \pmod{4}$

The 4 subscales will be calculated as follows:

• Transcendence (%) = sum of transcendence questions / 30

- Transcendence questions are those marked with a 'T' on questionnaire: 1, 7, 11, 13, 19, and 22
- Positive Mood (%) = sum of positive mood questions / 30
  - Positive Mood questions are those marked with a 'P' on questionnaire: 2, 8, 12, 17, 27, and 30
- Ineffability (%) = sum of ineffability questions / 15
  - Ineffability questions are those marked with an 'I' on questionnaire: 3, 10, and 29
- Mystical (%) = sum of mystical questions / 75
  - Mystical questions are those unmarked on questionnaire: 4, 5, 6, 9, 14, 15, 16, 18, 20, 21, 23, 24, 25, 26, and 28

The MEQ30 Total Score (%) will be calculated by summing all 30 questions and dividing by 150. A subject is considered to have had a 'complete mystical experience' when  $\geq 60\%$  of the maximum possible score is achieved on all 4 factor subscales.

Descriptive statistics for each of the 4 subscales and for the MEQ30 Total Score will be presented for actual values on Day 2. The number and percentage of subjects defined as having 'a complete mystical experience' will be provided. A by-subject listing will be provided for all MEQ30 responses, the 4 subscales and the MEQ30 Total Score.

## 6.4.4 **5D-ASC**

The 5D-ASC will be administered on Day 2 to retrospectively assess the subject's peak alteration of consciousness during the dosing session as compared with their normal waking consciousness. The 5D-ASC consists of 94 self-rated 100 mm VAS questions with anchors of 0 = 'no not more than usually' to 100 = 'yes more than usually'. The 94 items are combined into 5 subscales.

- 1. Oceanic boundlessness summation of questions 1, 3, 9, 12, 16, 18, 26, 34, 35, 36, 40, 41, 42, 45, 50, 52, 57, 62, 63, 69, 71, 73, 81, 86, 87, 91, and 94. Maximum value = 2700.
- 2. Anxious ego dissolution summation of questions 6, 8, 21, 27, 32, 38, 43, 44, 46, 47, 53, 56, 60, 64, 67, 78, 79, 80, 85, 88, and 89. Maximum value = 2100.
- 3. Visionary destructuralization summation of questions 7, 14, 20, 22, 23, 28, 31, 33, 39, 54, 58, 70, 72, 75, 77, 82, 83, and 90. Maximum value = 1800.
- 4. Auditory alterations summation of questions 4, 5, 11, 13, 19, 25, 30, 48, 49, 55, 65, 66, 74, 76, 92 and 93. Maximum value = 1600.
- 5. Vigilance reduction summation of questions 2, 10, 15, 17, 24, 29, 37, 51, 59, 61, 68, and 84. Maximum value = 1200.

The 5D-ASC Total Score will be calculated as the sum of all the questions. The maximum value for the Total Score is 9400.

Descriptive statistics for each subscale and the total score will be presented for each treatment arm. A figure showing the percent of maximum value for each subscale and total score by treatment arm will be provided. A listing of the 5D-ASC subscales and Total Score will be provided.

## 6.4.5 Treatment Assignment/Blinding Question

On Day 2, subjects will be asked to indicate which sentence they agree with most, using a 5-point Likert Scale:

- 1 = I am positive I received active drug
- 2 = I think I received active drug
- 3 = I cannot tell whether I received active drug or placebo
- 4 = I think I received placebo
- 5 = I am positive I received placebo

The number and percentage of subjects reporting each level will be presented. Also, the number and percentage of subjects correctly reporting (levels 1 and 2 for active drug or levels 4 and 5 for placebo) their treatment assignments will be reported. A listing will be provided.

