Multiple procedures have been included in this study to enhance subject safety. Subjects will undergo repeated eligibility assessments at Screening (Visit 1), Baseline (Visit 2), and prior to dosing on Day 1 (Visit 3A) to ensure the subject is fit to receive study drug. Additionally, based on the pharmacological profile of LSD, which includes alterations of perception and consciousness and the potential for development of acute anxiety, subjects will be continuously monitored during the Dosing Session for psychological and physiological well-being. Two Dosing Session Monitors will support the subject, and subjects will be under their observation at all times during the Dosing Session (either both in the session room, or one in the session room and one via live remote monitoring on site in a separate room). Additionally, based on the known autonomic effects of MM-120, serial measurement of vital signs (heart rate and blood pressure) will be collected throughout the Dosing Session. A detailed Dosing Session Monitor Manual and Participant Education Session Manual has been developed to provide subjects across clinical sites with consistent education about what to expect and consistent, continual monitoring during the Dosing Session.

Overall, the benefit-risk profile of LSD at doses up to 200 µg (freebase-equivalent) is favorable and supports development based on its prior safe clinical use in over 1000 subjects, well-characterized pharmacokinetics, pharmacodynamics and manageable transient physiological and psychological effects. Inclusion of the 4 planned doses in this Phase 2 dose-finding study (see Section 2.3) will enable optimal dose selection for Phase 3 clinical trials, aid in interpretation of study results in the context of potential functional unblinding and will enable further characterization of the mechanism of action of MM-120 (i.e., whether psychedelic effects are necessary for clinical benefit).

Refer to the MM-120 Investigator's Brochure for additional risk-benefit information.

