## 2.1.4 Exploratory Objectives

Exploratory objectives of the study include:

- To explore dose response on drug effects, altered perception and mystical experience,
- To explore the effect of MM-120 on direct and indirect health-care resource utilization (HCRU) and associated costs (for later analysis, not part of this SAP),
- To explore whether genetic polymorphisms are related to pharmacodynamics,
- To assess blind integrity and to examine whether guess rates are associated with outcomes such as AEs or mood/anxiety symptoms.

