## 3.2.1 Randomization Scheme and Treatment Arm Assignment

Subjects will be randomized in a 1:1:1:1:1 ratio to one of the 4 dose levels of IP or placebo. Randomization will be centrally performed by a Randomization Trial Management System (RTMS). The 5 treatment groups are:

- 1. 25 µg (freebase-equivalent) of MM-120
- 2. 50 µg (freebase-equivalent) of MM-120
- 3. 100 µg (freebase-equivalent) of MM-120
- 4. 200 µg (freebase-equivalent) of MM-120
- 5. Placebo

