## 9 SAMPLE SIZE AND POWER CALCULATIONS

A total sample of 180 subjects, 36 per arm, is required to ensure a mean power >87% for an MCP-Mod Analysis rejecting the hypothesis of a constant dose-response curve using the multiple comparisons procedure (MCP), assuming a null placebo response, a maximum standardized effect of 0.6 within the doses range, and a common standard deviation within the dose arms, if a studywise one-sided type-1 error rate <0.05 is required.

The analysis assumes 4 doses of active medication (25, 50, 100 and 200  $\mu$ g freebase-equivalent) and placebo. The required sample size for each arm is 36 subjects.

The R package Dose Finding (https://CRAN.R-project.org/package=DoseFinding) has been used to estimate the sample size and corresponding power. The power for each model is estimated as shown Table 6.

Table 6	Power by Mode

Model	Power (%)
Sigmoid Emax (ED50, hill)	
10, 1	84.5
100, 5	90.7
100, 10	91.0
150, 10	89.9
Emax (D50 = 100)	83.2
Linear	85.0

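### SAP 6.4.5 turns the blinding question into a percent-correct figure with no dose-versus-placebo contrast or interval; pooled over arms, expected values up to 80% fit an intact or a broken blind

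*SAP*

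**What the plan says.** SAP 6.4.5 takes one five-level answer from each subject on Day 2 and plans two summaries and a listing.

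- The distribution: "The number and percentage of subjects reporting each level will be presented".
- The derived measure: the "percentage of subjects correctly reporting (levels 1 and 2 for active drug or levels 4 and 5 for placebo) their treatment assignments will be reported". Level 3 (cannot tell) counts as correct in no arm.

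No chance reference, comparison between arms, interval or index is named. Section 6.4.5 does not mention treatment arm, whereas 6.4.4 does for the 5D-ASC. SAP section 4 supplies a default: summaries are by treatment group, with overall figures where appropriate.

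The question serves an exploratory objective in SAP 2.1.4: "To assess blind integrity and to examine whether guess rates are associated with outcomes such as AEs or mood/anxiety symptoms". Protocol 2.4 expects the four doses to "aid in interpretation of study results in the context of potential functional unblinding". On allocation, SAP 3.2.1 states: "Subjects will be randomized in a 1:1:1:1:1 ratio to one of the 4 dose levels of IP or placebo".

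For other binary outcomes the SAP goes further. HAM-A response and remission (6.4.1) and ASEX sexual dysfunction (6.3.10) each get the difference in rates between every dose and placebo with a 95% CI.

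**The concern.** Blinding fails when beliefs about treatment differ between arms. A percent-correct figure does not measure that difference directly. In a dose arm, correct means answering active; on placebo, correct means answering placebo. A general lean towards answering active therefore raises the figure in four arms and lowers it in one, whether or not the drug has revealed itself.

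The issue matters because the plan itself expects perceptible effects. Protocol Table 3 describes 100 and 200 µg as reliably psychedelic, and Protocol 8.4.5 bars session monitors from rating the CGI because they may be functionally unblinded. Belief that rises with dose is a rival explanation for a positive HAM-A dose-response, so a reader of the results will want to see how far belief differed from placebo at each dose, and how precisely that is known.

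**Working it through.** **Inputs.** SAP 9 gives the arm size: "A total sample of 180 subjects, 36 per arm, is required to ensure a mean power >87% for an MCP-Mod" analysis. So 5 × 36 = 180 subjects, 4 × 36 = 144 of them active, and the active share is 144/180 = 0.80. Section 6.4.5 states no figure to reproduce. The power table in SAP 9, which uses the same arm size, does reproduce with "a maximum standardized effect of 0.6 within the doses range" and one-sided 0.05: 84.6, 90.7, 91.0, 89.9, 83.2 and 85.1% by simulation, against 84.5, 90.7, 91.0, 89.9, 83.2 and 85.0% stated (mean 87.4% both ways). That confirms the arm size and says nothing about blinding. The documents give no guess rates, so every guess rate below is an assumption.

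**Pooled figure.** Pooled % correct = 0.8 × P(says active | active) + 0.2 × P(says placebo | placebo).

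*Intact blind, nobody unsure.* Every arm says active with probability g, so the figure is 0.8g + 0.2(1 − g) = 0.2 + 0.6g:

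| g | 0.5 | 0.6 | 0.7 | 0.8 | 0.9 | 1.0 |
|---|---|---|---|---|---|---|
| Pooled % correct | 50 | 56 | 62 | 68 | 74 | 80 |

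*Broken blind, same range.* With 77.5% of active and 90% of placebo subjects correct: 0.8 × 0.775 + 0.2 × 0.90 = 0.80. With 70% and 100%: 0.56 + 0.20 = 0.76.

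*Two assumed patterns with the same pooled value.*

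- A, intact: every arm 80% active, 10% unsure, 10% placebo. 0.8 × 0.80 + 0.2 × 0.10 = 0.66.
- B, dose-graded unblinding: 30, 50, 80 and 90% say active at 25, 50, 100 and 200 µg, and 80% of placebo subjects say placebo. (0.30 + 0.50 + 0.80 + 0.90 + 0.80)/5 = 0.66.

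**The same patterns by arm (% correct).**

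| Pattern | 25 µg | 50 µg | 100 µg | 200 µg | Placebo |
|---|---|---|---|---|---|
| A, intact | 80 | 80 | 80 | 80 | 10 |
| B, dose-graded | 30 | 50 | 80 | 90 | 80 |

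The 100 µg arm reads 80% in both, so one dose arm alone does not tell them apart. Set against placebo, the patterns are plainly different. If all arms guess alike, a dose arm's % correct plus the placebo arm's % correct equals 100 minus the % unsure. Pattern A gives 80 + 10 = 90. Pattern B gives 110, 130, 160 and 170, none of which identical guessing can produce in expectation.

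**The proposed contrast.** Difference = % at level 1 or 2 in the dose arm minus the same % on placebo.

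- Pattern A: 80 − 80 = 0 at every dose.
- Pattern B: at most 20% of placebo subjects can say active. If 10% do, the differences are 20, 40, 70 and 80 points; if 20% do, they are 10, 30, 60 and 70.

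**Precision.** Half-width = 1.96 × √{[p₁(1 − p₁) + p₀(1 − p₀)]/36}.

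- 0.80 v 0.80: 1.96 × √(0.32/36) = 0.18
- 0.80 v 0.50: 1.96 × √(0.41/36) = 0.21
- 0.95 v 0.30: 1.96 × √(0.2575/36) = 0.17
- 0.30 v 0.20: 1.96 × √(0.37/36) = 0.20, so a 10-point difference at the lowest dose would not be resolved.

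**Bang's index by arm** (share correct minus share incorrect). Pattern A gives +0.70 in each dose arm and −0.70 on placebo, summing to 0. The broken example with 77.5% and 90% correct and nobody unsure gives +0.55 and +0.80, summing to +1.35. The index must be read across arms, because a lean towards active moves it away from 0 within an arm even when the blind holds.

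**The case against.** The best defence is that nothing in the SAP says to pool. Section 4 makes presentation by treatment group the default and 6.4.5 does not override it. Tabulated that way, even the percent-correct figure separates patterns A and B, and the five-level table already contains the share at levels 1 and 2 in every arm, with level 3 as its own row. Bang's index can be calculated from that table. The item is exploratory and descriptive with no decision rule, and the Drug Effect VAS, MEQ30 and 5D-ASC from the same visit also bear on perceptible drug effect.

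Most of this stands. A reader might infer from 6.4.5 that the plan cannot tell an intact blind from a broken one, or that percent correct is its only blinding output. The documents do not support either reading: the first holds only for the pooled figure or for one dose arm read alone, and the second overlooks the five-level distribution. Even pooled, an expected value above 80% rules out an intact blind. Nor can the size of any lean towards active be put down to subjects knowing the 4:1 odds, since the documents reviewed do not show what subjects were told.

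What the defence leaves open is that 6.4.5 does not itself specify arms, and that the contrast and its uncertainty are left for the reader to work out, although the SAP prints both for other binary outcomes.

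**Conclusion.** The point holds as a gap in what is derived and reported. Pooled percent correct is ambiguous for expected values up to 80%, and within a dose arm it is only the believes-active rate. The by-arm distribution implied by SAP section 4 does carry the information, but no dose-versus-placebo difference or interval is planned from it.

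The 80% bound follows from the 4:1 allocation and needs no assumed guess rate beyond identical guessing in all arms. The 66% tie rests on two chosen patterns: it shows that the ambiguity is possible, not how likely it is. This is a cheap improvement to an exploratory analysis. It is not an error that leaves the blind-integrity objective unanswerable, and it does not affect the validity of the primary test.

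**What to change.** In SAP 6.4.5:

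- State that both summaries are by treatment arm.
- For each dose arm, add the difference from placebo in the percentage answering level 1 or 2, with a 95% CI, where 0 means that guesses do not differ from placebo; and/or report Bang's blinding index by arm with a 95% CI, read across arms.
- Keep level 3 as a separate category.
- Do not interpret a percent correct pooled over arms.

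The cost is a sentence or two and one table from data already collected, in the format of 6.4.1 and 6.3.10. The downside is precision: about ±17 to 21 points per contrast at 36 per arm, so an interval that includes 0 should not be read as proof of an intact blind. If the change is made after unblinding, it should be labelled ad hoc, as the SAP addendum does for its own additions. The second half of the objective, relating guesses to outcomes, also has no analysis in 6.4.5; that is a separate gap which this change does not close.

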#### 6.5 Subgroup Analyses

Descriptive statistics, including 95% CIs for the HAM-A Total Score change from baseline at Week 1, Week 2, Week 4, Week 8 and End of Study will be provided by the following subgroups:

- Baseline HAM-A Total Score:  $\leq$  median baseline value, > median baseline value
- Age:  $\leq$ 35 years, > 35 years
- Sex: male, female
- Race: white, non-white

#### 7 SAFETY ANALYSIS

Safety assessments include adverse events, laboratory parameters, vital signs, electrocardiograms, physical exams and the Columbia Suicide Severity Rating Scale (C-SSRS). All safety summaries will be conducted using the safety (SAF) population and will be presented by treatment group. No formal hypothesis testing will be performed to compare differences between treatment groups.

#### 7.1 Extent of Exposure

Subjects will be dosed 1 time during this study, consisting of 8 capsules. Descriptive statistics for the total number of capsules taken will be provided by treatment group.

In addition, the number and percent of subjects (or '0' if no subjects encounter such an event) with any of the following special situations for study drug administration will be provided:

- Medication error or incorrect drug administration
- Overdose
- Deliberate abuse
- Drug interaction
- Occupational exposure
- Breastfeeding with suspected infant exposure
- Drug accountability issue

A listing of all subject exposure data will be provided.

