9.3. Adverse Events of Special Interest

AESIs are a subset of AEs that are suggestive of abuse potential (including Central Nervous System-related and drug abuse-related) and any special situations defined in Section 9.9 that have an associated AE or drug accountability discrepancy (see Section 6.7).

The AE terms listed below are MedDRA Preferred Terms to be used in classifying Adverse Events of Special Interest (AESIs) related to abuse liability when deemed appropriate by the PI (or designee):

- Euphoria-related terms: Euphoric mood; Elevated mood; Feeling abnormal; Feeling drunk; Feeling of relaxation; Dizziness; Thinking abnormal; Hallucination; Inappropriate affect.
- Terms indicative of impaired attention, cognition, and mood: Somnolence; Mood disorders and disturbances.
- Dissociative/psychotic terms: Psychosis; Aggression; Confusion and disorientation.
- Overdose-/ Misuse-related terms not captured elsewhere: Drug tolerance; Habituation; Drug withdrawal syndrome; Substance-related disorders.

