9.9. Special Situations

Special situations with study drug are defined as the following:

- Medication error or incorrect drug administration
- Overdose (exceeds the protocol-specified maximum; see Section 9.5 for the definition of overdose)
- Deliberate abuse
- Deliberate misuse
- Drug interaction
- Occupational exposure

Clinical Study Protocol: MMED008

- Breastfeeding with suspected infant exposure
- Drug accountability issue (e.g., diversion) if linked to an AE (see Section 6.7)

If any of these special situations with study drug occur, they will be reported on the special situations with study drug eCRF page, even if there is no accompanying AE. All clinical manifestations in relation to these special situations (as defined above) will be reported as an SAEs or AESIs at the same time using the corresponding section of the eCRF.

For example, if a medication error or interaction occurred, the Investigator will assess whether to consider an AE to have occurred, and if so, will assign the possible relationship to the study drug.

Additional information may be requested by the site including all AE information and all triggering drug accountability discrepancies.

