## 7.2.5 Adverse Events of Special Interest

Adverse events of special interest (AESI) are defined as a subset of AEs that are suggestive of abuse potential and any special situations defined in Section 9.9 of the protocol that have an associated AE. The following MedDRA Preferred Terms will be used to classify AESIs related to abuse liability:

• Euphoria-related terms: Euphoric mood; Elevated mood; Feeling abnormal; Feeling drunk; Feeling of relaxation; Dizziness; Thinking abnormal; Hallucination; Inappropriate

affect.

- Terms indicative of impaired attention, cognition, and mood: Somnolence; Mood disorders and disturbances.
- Dissociative/psychotic terms: Psychosis; Aggression; Confusion and disorientation.
- Overdose- / Misuse-related terms not captured elsewhere: Drug tolerance; Habituation; Drug withdrawal syndrome; Substance-related disorders.

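### The SAP's special-situation table and AESI definition do not match the protocol: deliberate misuse has no row, and the AESI rule differs in two respects

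*SAP*

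**What the plan says.** **Special situations.** SAP 7.1 (Extent of Exposure) will give the number and percentage of subjects "with any of the following special situations for study drug administration will be provided", printing a zero where a category is empty. It lists seven categories, including "Deliberate abuse" and, without condition, "Drug accountability issue". Protocol 9.9 lists eight. It has a separate entry, "Deliberate misuse", and its accountability entry is conditional: "Drug accountability issue (e.g., diversion) if linked to an AE (see Section 6.7"). Protocol 9.9 also sends every special situation to its own eCRF page, with or without an AE.

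**AESI definition.** Protocol 9.3 includes "any special situations defined in Section 9.9 that have an associated AE or drug accountability discrepancy". SAP 7.2.5 includes "any special situations defined in Section 9.9 of the protocol that have an associated AE" and stops there.

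**AESI classification.** Both sections print the same list of terms. Protocol 9.3 applies it "when deemed appropriate by the PI (or designee"). SAP 7.2.5 says the terms will be used for classification and mentions no investigator judgement.

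**Outputs.** SAP 7.2.6 reports treatment-emergent AESIs in the overall summary and by SOC and PT. SAP Section 8, which covers changes from the protocol, mentions none of these differences. The SAP addendum says it leaves the pre-planned analyses unchanged.

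**The concern.** The protocol handles MM-120 as a Schedule I drug with diversion controls (Protocol 6.7), and sites must report AESIs suggestive of abuse potential within 24 hours (Protocol 9.4.2). A reader of the study report will expect the special-situation table to cover every category that sites were asked to record, and the AESI table to describe the same events that sites reported.

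Followed as written, the SAP does neither. A table that undertakes to print zeros cannot state even a zero for deliberate misuse. The AESI table is built on a rule that differs from the one sites worked under, so expedited reports, narratives and tables may not reconcile, and nothing in the SAP tells the reader why.

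**Working it through.** No power, alpha or event figure bears on this point, so the check is a comparison of lists and rules.

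**Step 1: special situations (Protocol 9.9 against SAP 7.1)**

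| Category | Protocol 9.9 | SAP 7.1 |
|---|---|---|
| Medication error or incorrect administration | yes | yes |
| Overdose | yes | yes |
| Deliberate abuse | yes | yes |
| Deliberate misuse | yes | **no** |
| Drug interaction | yes | yes |
| Occupational exposure | yes | yes |
| Breastfeeding with suspected infant exposure | yes | yes |
| Drug accountability issue | only if linked to an AE | yes, no condition |
| Count | 8 | 7 |

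8 − 7 = 1 category is missing. On the last category the SAP is wider than the protocol.

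**Step 2: the AESI route for special situations (Protocol 9.3 against SAP 7.2.5)**

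| Special situation with | AESI, Protocol 9.3 | AESI, SAP 7.2.5 | Counted in SAP 7.1 |
|---|---|---|---|
| an AE | yes | yes | yes, except misuse |
| a discrepancy, no AE | yes | no | yes, except misuse |
| neither | no | no | yes, except misuse |

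Only the second line changes AESI status. SAP 7.2.5 refers back to Protocol 9.9, so misuse with an AE, or an accountability issue with an AE, is still an AESI. The sharpest case is deliberate misuse with missing capsules (a discrepancy named in Protocol 6.7) and no AE. Under the protocol it is an AESI. Under the SAP it is not, it has no misuse row, and at most it falls under the general accountability row.

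**Step 3: the term list**

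Counting terms by group, in both documents: 9 euphoria-related + 2 attention, cognition and mood + 3 dissociative/psychotic + 4 overdose/misuse = 18. The lists are identical; the rule for applying them is not. The protocol's set is the listed events that the investigator also judges appropriate. Read as written, the SAP's set is all listed events. The first is contained in the second, so among treatment-emergent events the SAP's count on this route is equal or larger.

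The gap depends on how often investigators decline to flag a listed event. Neither document gives a rate. Protocol 2.3 and 2.4 do expect hallucinations, and Hallucination is a listed term, so there is room for a gap, but its size by dose is unknown.

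**The case against.** The strongest reply is that little is lost. Every TEAE is tabulated by SOC and PT and by PT alone, by treatment group, so rates of the listed terms are visible under either AESI rule. Misuse with an AE still qualifies as an AESI, and SAP 7.2.5 keeps the misuse-related terms. The dose is single, witnessed and followed by a mouth-and-hands check (Protocol 6.8), which limits the opportunity for misuse. The protocol promises no special-situation summary table, so no promised output is withdrawn. All of this stands, and it keeps the point minor.

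Two further replies stand in part. Protocol 9.3 itself opens by calling AESIs a subset of AEs, so a discrepancy without an AE sits awkwardly there and the SAP's wording may be the more coherent. And SAP 7.2.5 does not say whether an investigator flag is also used, so list-only classification is a reading of its silence. Both replies show that the definition needs settling; neither settles it.

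A reader might infer that the SAP is narrower than the protocol throughout, or that diversion without an AE vanishes from the report. The documents do not support this: SAP 7.1 counts accountability issues without the AE link, and dropping the judgement condition can only add listed events. A reader might also infer that AESI rates will diverge widely at the higher doses, or that AESI incidence is the trial's abuse-potential read-out. No figure supports the first, and Protocol Section 3 contains no abuse-potential objective to support the second.

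**Conclusion.** The inconsistency is real and minor. One of eight protocol-defined special situations has no row in a table that promises zeros. Special situations with an accountability discrepancy but no AE are AESIs in the protocol and not in the SAP. The same 18 terms are applied with investigator judgement in one document and with no stated judgement in the other, so the SAP's count on that route can equal or exceed the site-reported set. SAP Section 8 records none of these differences.

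This rests on reading SAP 7.2.5 as written, with the list alone deciding, and on investigators flagging only listed terms. No effect in subjects or percentages can be given. The primary analysis, alpha and sample size are unaffected.

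**What to change.** 1. Add a deliberate misuse row to the SAP 7.1 table.
2. Reconcile Protocol 9.3 and SAP 7.2.5 to one AESI definition. State that the tabulated AESI is the term list applied to all TEAEs, which is the plain reading of the present SAP.
3. Count any special situation with an accountability discrepancy but no AE on a separate line. It has no SOC or PT, so restoring the protocol's words in SAP 7.2.5 would not by itself bring it into the SOC/PT table.
4. Record the remaining differences in SAP Section 8, including the unconditional accountability row.

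A second column for investigator-flagged AESIs would help reconciliation with site reports, but is optional.

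The cost is one table row, one count line and a few sentences of SAP text, with a short clarification to Protocol 9.3. Special situations already have their own eCRF page, so the misuse row needs no new data collection.
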